1. PROTOCOL SYNOPSIS

Title	Randomised placebo-controlled study of grass pollen allergen immunotherapy tablet (AIT) for seasonal rhinitis: time course of nasal, cutaneous and immunological outcomes
Short title	Grass Pollen Allergen Immunotherapy Tablet (AIT) Time Course Study
Conducted by	Royal Brompton Hospital and Imperial College
Protocol Chair	[name], MA, FRCP
Accrual Objective	50 participants with moderate-severe grass pollen allergic rhinitis; 20 healthy, non-atopic participants
Study Design	
A randomized, double-blind, single-centre, placebo-controlled, two-arm time course study comparing grass pollen AIT with placebo.
 
The study will involve a 4 month recruitment phase, a 12 month randomized, blinded treatment phase (Phase I), and finally a further 12-24 months open treatment phase and a 12 month follow up after withdrawal of treatment (Phase II). Up to 50 grass pollen allergic (atopic) participants will be enrolled to ensure randomisation of at least 44. Further we shall recruit 20 healthy, non-atopic volunteers.
 
Individuals with severe grass pollen hay fever, with or without associated seasonal asthma, will be recruited after the 2013 grass pollen season, between December 2013 and April 2014. Screening will be completed before eligible atopic participants are randomized to one of the following two treatment arms in a 1:1 ratio:
 
• Grass pollen AIT• Placebo AIT

2. GENERAL ANALYSIS AND REPORTING CONVENTIONS

The following analyses and reporting conventions will be used:

- Categorical variables will be summarized using counts (n) and percentages (%) and will be presented in the form “n (%).” Percentages will be rounded to one decimal place.
- Numeric variables will be summarized using n, mean, standard deviation (SD), median, minimum (min), maximum (max). Descriptive statistics will be displayed in the order: n, mean, SD, median, min, max.
- The median will be reported as the average of the two middle numbers if the dataset contains an even number of observations.
- Test statistics such as *t* test statistics will be reported to two decimal places.
- *P*-values will be reported to three decimal places if greater than or equal to 0.001. If less than 0.001, the value will be reported as “<0.001.”

If departures from these general conventions are present in the specific evaluations section of this SAP, then those conventions will take precedence over these general conventions.

3. ANALYSIS SAMPLES

- **Intent-to-treat (ITT) sample** will be defined as all randomized participants. ITT participants will be analyzed with the group to which they were randomized, regardless of the medication actually received. If participants drop out post-randomization, they will be invited to complete study assessments throughout the duration of the trial.
- **Per-protocol (PP) sample** will be defined as ITT sample participants who remain in the study until the primary endpoint was assessed. Participants in the PP sample must be compliant with study medication, defined as taking 75% or more of their study medication for the duration of the study. Compliance with study medication will be assessed by pill count for SLIT and placebo. Participants in the PP sample will be analyzed with the group to which they were randomized.
- **Safety sample (SS)** will be defined as all enrolled participants. Participants in the safety sample will be analyzed in regards to adverse events.

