6.8.2 Analysis samples

- **Intent-to-treat (ITT) sample** will be defined as all randomized participants. ITT participants will be analysed with the group to which they were randomized, regardless of the medication actually received. If participants drop out post randomisation, they will be invited to complete study assessments throughout the duration of the trial.
- **Per-protocol (PP) sample** will be defined as ITT sample participants who remain in the study for 12 months and in whom the primary endpoints were assessed. Participants in the PP sample must be compliant with study medication, defined as taking 75% or more of their study medication for the duration of the study. Compliance with study medication will be as assessed by pill count for AIT/placebo. Participants in the PP sample will be analysed with the group to which they were randomized.
- **Safety sample (SS)** will be defined as all randomized participants who received at least one dose of study medication. Participants in the safety sample will be analysed with the group according to the medication they actually received, regardless of their randomized assignment.

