8. SAFETY EVALUATION

8.1 Overview of Safety Analysis Methods

All safety analyses will be carried out using the safety sample defined in Section 3. Missing safety information will not be imputed. Safety will be analyzed through the reporting of adverse events (AEs).

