8.2 Adverse Events

Side effects to the treatment will be recorded daily according to the WAO guidelines. They will be recorded as an Adverse Event (AE) only when the severity of the symptoms has a > Grade 1 according to WAO guidelines.

All AEs will be classified using the National Cancer Institute's (NCI's) Common Toxicity Criteria for Adverse Events (CTCAE). This will be performed by the AIT study team. Each AE is entered on the case report form (CRF) once at the highest severity and the duration of the AE will be recorded. Also information about System Organ Class – Term and CTCAE Term – Term will be included.

CTCAE classification version 4.03: http://evs.nci.nih.gov/ftp1/CTCAE/CTCAE_4.03_2010-06-14_QuickReference_8.5x11.pdf will be used by the AIT team and send to the Inform database via excel files.

An overall summary table will be developed to report the number of events and the number and percentage of subjects having at least one event in the following categories:

- AEs
- AEs indicated as serious
- AEs that lead to study drug discontinuation
- AEs with an outcome of death
- AEs that were reported as being related to a study drug
- AEs reported by maximum severity

Exploratory analysis will be carried out for the different type of adverse events to compare the intervention with control group: frequency tables, bar graphs, summary statistics.

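### The SAP's safety sample and its adverse-event filter both depart from the protocol and need to be reconciled with it

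*SAP*

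**What the plan says.** **Safety sample.** Protocol 6.8.2 states that the safety sample "will be defined as all randomized participants who received at least one dose of study medication", and that its members are "analysed with the group according to the medication they actually received". SAP section 3 states that it "will be defined as all enrolled participants" and adds only that they will be analysed for adverse events (AEs). For the ITT and per-protocol samples, SAP 3 does carry over the protocol's grouping rule; for the safety sample it gives none. SAP 8.1 sets the scope: "All safety analyses will be carried out using the safety sample defined in Section 3".

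Two outputs in SAP 8.2 rest on this sample. The first is a summary: "An overall summary table will be developed to report the number of events and the number and percentage of subjects", with rows for events related to study drug, events leading to its discontinuation, and "AEs reported by maximum severity", among others. Its layout (pooled or by arm) is not stated. The second is an exploratory set of displays "to compare the intervention with control group: frequency tables, bar graphs, summary statistics".

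**AE filter.** SAP 8.2 records side effects of treatment as AEs "only when the severity of the symptoms has a > Grade 1 according to WAO guidelines", and then classifies all AEs by CTCAE. In the protocol, section 6.7.1.2 exempts one set of tablet effects from reporting: oral itching and mild swelling, as long as they do not interfere with daily activities or sleep. Section 6.7.6.2 collects whatever 6.7.1.1 and 6.7.1.2 do not exclude, starting at screening, and 6.7.6.3 has AEs recorded whatever their severity.

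**The concern.** The two safety samples differ in substance. Both documents distinguish enrolled atopic participants (up to 50) from randomised ones (at least 44), so the SAP's set can contain people who never received a tablet. They cannot have a drug-related event or stop a drug they never took, yet they would count in the denominator of those percentages. The SAP also has no rule for a participant who takes the other arm's tablets, although it plans to compare the arms. It gives no reason for leaving the protocol's definition and does not say that it overrides it.

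The filter concerns which events become AEs at all. Secondary objective 3 (Protocol 5.2) is to document the presence and severity of local and systemic side effects, and Protocol 6.7.6.8 tabulates AEs by severity and treatment relatedness. A filter wider than the protocol's exemption takes mild events out of those tables. Two analysts, one following each document, would produce different safety tables from the same trial.

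**Working it through.** The plan gives no figure on this point to reproduce. The checks are a denominator calculation and a comparison of the recording rules.

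**1. Pooled summary table.** Inputs: up to 50 atopic participants enrolled and at least 44 randomised (Protocol 2, SAP 1). For an event that only dosed people can have:

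relative dilution = 1 − dosed / denominator

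- All 50 dosed: 1 − 50/50 = 0%.
- 44 dosed, 6 never dosed: 1 − 44/50 = 12%.

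Absolute change = 12% × true rate. The rates below are assumptions, because the documents give no AE rate for this trial.

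| Assumed rate among dosed | Reported over 50 | Change |
|---|---|---|
| 10% | 8.8% | 1.2 points |
| 25% | 22.0% | 3.0 points |
| 50% | 44.0% | 6.0 points |

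The number of drug-related events is the same under either definition; only the percentage moves.

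**2. By-arm tables.** Someone never randomised has no arm and cannot enter these. The arm figures change in two situations only.

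- *Randomised but undosed.* In an arm of 22 (44/2), one such person gives 1 − 21/22 = 4.5% relative dilution and two give 1 − 20/22 = 9.1%. One person is worth 0.5 points at a 10% rate and 2.3 points at 50%. Such a person is possible: Protocol 6.5.14 places randomisation at Visit 0a, and 6.4.3 places the first tablet at Visit 1, one day after Visit 0b. Protocol 6 instead places randomisation after the baseline visit, which leaves a shorter gap. No passage shows that such a person exists.
- *Took the other arm's tablets.* Under Protocol 6.8.2 the participant and any events move to the arm received. Under SAP 3 no rule applies.

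**3. Recording rules for tablet effects.** Grades for local reactions are those of Protocol 6.7.2, Table 6. Grade 1 there means not troublesome, untreated and no discontinuation.

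| Tablet effect | Protocol | SAP 8.2 |
|---|---|---|
| Oral itching or mild swelling, Grade 1 | Exempt if not bothersome | Not an AE |
| Oral itching or mild swelling, treated, no interference with activities or sleep (Grade 2) | Exempt | AE |
| Throat irritation or gastrointestinal symptoms, Grade 1 | AE | Not an AE |
| Same symptoms, Grade 2 or 3 | AE | AE |
| Systemic reaction, Grade 1 | AE | Not stated |

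The rules nearly agree in the first row. The SAP is stricter in the second, because it captures an event that the protocol exempts. It is looser in the third. In the last row it is silent, because it does not say whether its WAO grade is the local scale only. No grade distribution is given, so the number of AEs lost cannot be estimated.

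**The case against.** The best defence of the wider sample is that AEs are collected from screening, and that nasal challenge, intradermal testing and biopsy take place before the first tablet and also in the controls. A dosed-only set used for everything would drop procedure events in people never dosed. This stands, and it is a reason to display those events separately. It does not justify putting never-dosed people in the denominator for drug-related events.

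It can also be said that the consequence is small: non-randomised people do not touch the arm comparison, the dilution needs a pooled table, and a drug-related percentage pooled over active and placebo tells little about either arm. That is fair and limits the size of the point.

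On the filter, the defence is that it follows a sentence on daily recording, that exploratory endpoint 3 (SAP 7.3.1) grades local symptoms daily and has a category for other symptoms, and that the diary in Appendix 9 asks about these. In context the filter may be meant for local diary symptoms only. This also stands: mild symptoms are not lost to the trial. The mismatch for Grade 1 throat and gastrointestinal symptoms remains even so.

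Three stronger readings might be inferred, and the documents do not support them.

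- *The severity table would start at Grade 2.* The filter uses a WAO grade and AEs are then classified by CTCAE, with no mapping between the scales. An event that passes the filter need not be CTCAE Grade 2.
- *Mild systemic reactions are certainly excluded.* The SAP does not say so.
- *The 20 controls swell the denominator to 70.* Enrolled is not defined, and both documents speak of enrolling atopic participants but recruiting controls.

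**Conclusion.** Both mismatches hold on the text and should be corrected. The safety sample in SAP 3 contradicts Protocol 6.8.2 on who is included and omits the as-received rule, and SAP 8.1 applies it to all safety analyses. The AE filter in SAP 8.2 is wider than the protocol's tablet exemption for Grade 1 throat and gastrointestinal symptoms and narrower for treated oral symptoms that do not interfere with activities or sleep.

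The size is modest. The 12% relative dilution is an illustration that assumes 50 enrolled, 44 dosed and a pooled table. It is not an upper bound, because any randomised participant left undosed could take the number dosed below 44; it is zero if everyone enrolled is dosed. By-arm percentages are unaffected unless someone is randomised but undosed or takes the other arm's tablets. Efficacy results do not change. The effect of the filter cannot be quantified from the documents. Confidence is high that the texts conflict, and lower on how far any reported percentage would move.

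**What to change.** In SAP 3, restore the protocol's safety sample (randomised, at least one dose, grouped by medication received) for all treatment-related AE tables. In SAP 8.2, state that the summary table is shown by arm. List events in never-dosed atopic participants and in non-atopic controls separately, so that events collected from screening onward are kept.

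In SAP 8.2, reconcile the filter with Protocol 6.7.1.2, 6.7.6.2 and 6.7.6.3. State that it applies only to the exempted oral symptoms and not to systemic reactions, name the grading scale used for the filter and for the severity row, and settle how treated but non-interfering oral symptoms are handled. A cross-reference to exploratory endpoint 3 would show where mild local symptoms are reported.

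The cost is SAP wording and minor table work. The diary already asks about other symptoms, and SAP 10.2.1 schedules AE recording at the visits. Reported AE percentages may be slightly higher.

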4. UNBLINDING THE TRIAL FOR ANALYSIS PURPOSES

We will unblind the trial for analysis purposes after the 12 months blinded phase of this trial. The trial will be unblinded by the statistician, [name]. [name] will request and receive the unblinding list from the Inform Database team. Documentation will be performed when the randomization code was requested and provided, when the list was opened and when the randomization data was applied to the analysis dataset. This will include the time as well as the date. The documentation will be filed in the trial master file on file notes accordingly. Please also refer to SOP AIT009.

5. STUDY SUBJECTS

5.1 Demographic and Other Baseline Characteristics

Summary descriptive statistics for baseline and demographic characteristics will be reported for the randomized atopic and non- atopic sample.

Demographic data will include and data will be adjusted for age, gender, Skin Prick test (screening), specific IgE (screening) and compliance.

Furthermore the following characteristics will be used for descriptive statistics only: baseline visual analogue scale (How has your Hayfever been overall in the previous season? (Appendix 2 from Protocol), Polisensitisation (this will be defined as a positive skin prick test during screening apart from skin prick test to timothy grass and the positive control (Yes/No), seasonal asthma, this information will be taken from the medical and allergy history from the participant (Yes/No), total IgE, BMI, ethnicity.

These data will be presented in the following manner:

- Continuous data (e.g., age) will be summarized descriptively by mean, SD, median, min, and max.
- Categorical data (e.g., sex and ethnicity) will be presented as frequencies and percentages.

Demographic and baseline characteristic data will also be presented in data listings by study group (atopic (placebo and active group) and non-atopic).

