6.1 Primary endpoint

The area under the curve (AUC) of the early phase response (total nasal symptom score, TNSS, 0-60 minutes) following grass pollen nasal allergen challenge in active versus placebo-treated atopic participants at 12 months.

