6.8.3. Analysis of Endpoints

Analysis of study data will be conducted to address all objectives of the trial and other interrelationships among all data elements of interest to the investigators and of

relevance to the objectives of the study. Primary analysis of treatment effect will be conducted under the intention-to-treat (ITT) principle of eligible patients, whereby outcome data from all eligible patients will be included regardless of treatment compliance. In addition to the analyses described in sections below, summary descriptive statistics will be provided in the following manner: continuous data will be summarized descriptively by mean, standard deviation, median, and range; categorical data will be presented as enumerations and percentages.

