6.2 Treatment Compliance

Treatment compliance will be summarized by treatment arm through the total duration of blinded study therapy (12 months). In each of the treatment arms compliance rate will be calculated as follows: first we calculated the amount of days the participant should have taken the tablet from the start of the IMP until the last day of the IMP taken before switching to the open-label follow up treatment with Grazax. Then we calculated how many days the participant took the tablet according to the returned tablets counted by Pharmacy. We calculated the resulting difference between the amount of tablets that the participant should have taken to the actual amount of tablets taken (e.g. if the participant should have taken 100 tablets and he took 80 tablets it will be calculated as follows: $100:100 \times 80 = 80$ (this would be a compliance of 80 %).

Treatment compliance will be presented across treatment groups.

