7.2 Primary Endpoint

7.2.1 Analysis of the primary endpoint

The primary endpoint is the total nasal symptoms score (TNSS) measured at 0, 5, 15, 30 and 60 minutes (Early phase response (EPR)) following grass pollen nasal allergen challenge at 12 months (Appendix 6).

The endpoints will compare the following groups:

- SLIT versus SLIT Placebo
- SLIT versus SLIT Placebo versus non-atopic controls

This study requires the analysis of longitudinal data since the outcome of interest is measured over a period of time. Longitudinal analysis allows estimating the marginal effect of the predictors of interest such as Age, Gender, Skin Prick test, specific IgE, baseline visual analogue scale and compliance as well as the comparison between the intervention and control group. Longitudinal analysis also allows the assessment of changes over time. One of the comparisons of interest is the difference between the intervention and control groups at baseline, 6 months and 12 months. The other relevant comparison is the average EPR at 12 months with baseline for both groups. Longitudinal data require special statistical methods because observations made on each subject are correlated. This correlation must be taken into account to draw valid statistical inferences. Some of the approaches that model the correlation structure in longitudinal data are Models for the Mean response and Random coefficient models.

Also, before the main analysis exploratory analysis will be carried out: box plots, scatter plots, cross-tabs, frequency tables and summary statistics.

This will be analysed using the ITT sample and for the PP analysis population.

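### The SAP adjusts the ITT comparison for tablet compliance, a post-randomisation variable, so the 12-month active-versus-placebo difference is in general no longer the effect of assignment

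*SAP*

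**What the plan says.** The adjustment list is in SAP 5.1: "Demographic data will include and data will be adjusted for age, gender, Skin Prick test (screening), specific IgE (screening) and compliance". No condition is attached. SAP 7.2.1, on the primary endpoint, speaks of "predictors of interest such as Age, Gender, Skin Prick test, specific IgE, baseline visual analogue scale and compliance" and then gives the analysis sets: "This will be analysed using the ITT sample and for the PP analysis population". Of the contrasts to be drawn it says: "One of the comparisons of interest is the difference between the intervention and control groups at baseline, 6 months and 12 months".

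SAP 6.2 explains how compliance is obtained. The days on which a tablet was due are counted from the start of study medication to the last day before the open-label switch. "Then we calculated how many days the participant took the tablet according to the returned tablets counted by Pharmacy".

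Both documents commit to ITT. SAP 3: "ITT participants will be analyzed with the group to which they were randomized, regardless of the medication actually received". Protocol 6.8.3: "Primary analysis of treatment effect will be conducted under the intention-to-treat (ITT) principle of eligible patients"; it goes on to say that outcomes count whatever the participant's compliance. The endpoint in protocol 6.1 is the TNSS AUC "following grass pollen nasal allergen challenge in active versus placebo-treated atopic participants at 12 months". Protocol 6.8.3.1 tests it by ANOVA without naming compliance, and protocol 6.8.1 mentions only treatment effect, baseline values and visit number.

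SAP 7.3, 7.3.1 and 7.3.2 apply the primary-endpoint methodology to the secondary, exploratory and mechanistic endpoints. The SAP nowhere states a primary model without compliance.

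**The concern.** Randomisation balances the arms on what precedes it, not on what follows. If tablet-taking depends on the assigned tablet, and people who take more tablets would have had different AUCs anyway, holding tablet-taking fixed compares unlike participants. The ITT rules in SAP 3 and protocol 6.8.3 keep everyone in the assigned arm; conditioning on tablets taken then defeats their purpose while the label stays.

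An arm gap is plausible from the protocol itself. Section 6.4.1 reports oral itching and swelling in 50% to 60% of individuals, and withdrawal of 5% against 3% on placebo in an earlier trial.

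At stake is the trial's main result, with a distortion whose direction cannot be known before unblinding. SAP 7.2.1 also compares the arms at baseline. Adjusting that contrast for later compliance could create a difference where randomisation implies none.

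**Working it through.** **1. Algebra.** In a linear model with arm and compliance as main effects:

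adjusted difference = unadjusted difference - b x (mean compliance on active - mean compliance on placebo),

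where b is the pooled within-arm slope of AUC on compliance. The two agree only if b or the gap is zero.

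**2. The plan's own figures (protocol 6.8.1).** Mean AUC 4.63, SD 1.65, 22 per group, 80% power for a 30% reduction. The planned effect is 0.30 x 4.63 = 1.389. The sample size is 2 x (1.960 + 0.842)^2 x (1.65/1.389)^2 = 22.1, or 23 rounded up. Power at 22 per group is 79.7% by the normal approximation and 77.9% by the t distribution. The stated figure reproduces to within rounding.

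**3. Size under assumed inputs.** The documents give no arm gap, compliance SD or compliance-outcome correlation, so all three are assumed. Let rc be the correlation of compliance with underlying nasal reactivity and ra that of reactivity with AUC; compliance SD is 12 points. With no drug effect and the link present in both arms:

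shift = gap x 1.65 x ra x rc / 12,

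and half of that if the link exists in one arm only. For example, 10 x 1.65 x 0.5 x (-0.5) / 12 = -0.344. A positive gap means lower compliance on active; a negative shift favours active. Type I error is from simulation of 22 per arm, regressing one 12-month AUC on arm and compliance.

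| Gap (points) | rc / ra | Link in | Shift | % of 1.389 | Type I error |
|---|---|---|---|---|---|
| 5 | -0.3 / 0.5 | active only | -0.05 | 4% | 5.3% |
| 5 | -0.3 / 0.5 | both arms | -0.10 | 7% | 5.4% |
| 10 | -0.5 / 0.5 | active only | -0.17 | 12% | 6.1% |
| 10 | -0.5 / 0.5 | both arms | -0.34 | 25% | 9.6% |
| 10 | -0.7 / 0.7 | both arms | -0.67 | 49% | 28.3% |
| -10 | -0.5 / 0.5 | both arms | +0.34 | 25% | 9.9% |
| 0, or no link | | | 0 | 0% | about 5% |

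Without compliance in the model the bias is 0 and the error 5% throughout. A second set of assumptions (compliance SD 10, gap 5 or 10, reactivity-AUC correlation 0.6, reactivity-compliance correlation -0.3 or -0.6) gave shifts of -0.15 to -0.59 and type I error up to 19.9%.

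**4. Power for a true effect of -1.389.** Unadjusted, 78%. With a 10-point gap and no link there is no bias, but the variance is inflated by (144 + 25)/144 = 1.17; the mean standard error rises from 0.495 to 0.545 and power falls to 70%. With the link in both arms at +0.5/0.5 the estimate is -1.389 + 0.344 = -1.045 and power 49%. At -0.5/0.5 the estimate is -1.733 and power 89%, the gain being bias.

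**5. Which contrast.** In a random-intercept model over 0, 6 and 12 months, with arm by visit plus a compliance main effect (gap 10, -0.5/0.5, both arms), the 12-month arm difference moved by -0.33. The change-from-baseline contrast was unaffected with complete data.

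**6. Three-group comparisons.** Non-atopic controls are not randomised to tablets (protocol 6.3.8) and have one visit after screening (protocol 6), so they have no compliance value. By entry criteria (protocol 6.3.2) their grass-specific IgE (below 0.35 against at least 0.7 ISU) and grass skin prick result (negative against a wheal of at least 3 mm) do not overlap with the atopic arms. If the list is carried over, these models cannot be fitted meaningfully.

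**The case against.** Five points can be made on the other side.

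- **Baseline is ignored in the illustrations.** Protocol 6.8.1 says baseline values are taken into account, and baseline AUC would absorb part of the link. That is right, but the bias only shrinks. With baseline AUC as a covariate, the -0.34 case becomes -0.28, -0.18 or -0.11 for assumed baseline-to-12-month correlations of 0.25, 0.5 or 0.7. The -0.67 case becomes -0.45 at 0.49 and -0.27 at 0.7.
- **The 10-point gap has no source.** This stands. If each withdrawal in the 5% versus 3% figure counted as zero compliance, the gap would be at most 2 points, or 2 x 1.65 x 0.25 / 12 = 0.07 AUC units (5% of 1.389) at -0.5/0.5. Poor tablet-taking without withdrawal could add to it. The larger scenarios are not forecasts.
- **The model is not fixed.** SAP 7.2.1 gives its predictors as examples and does not choose a model, and the protocol's ANOVA names no compliance term. But SAP 5.1 states the adjustment outright, and nothing in the SAP offers an ITT model without it.
- **A change contrast escapes the problem.** Only with complete data: when 12-month dropout depended on compliance, adding compliance moved that contrast too (from -0.108 to -0.066 in one large simulated dataset). The protocol's primary contrast is in any case the 12-month difference between arms.
- **The three-group point is separate.** It is conditional on the list being carried over, and the IgE and skin prick part concerns screening variables. It does not bear on the ITT conflict.

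**Conclusion.** The concern holds. SAP 5.1 and 7.2.1 put a post-randomisation variable into an ITT analysis, against SAP 3 and protocol 6.8.3, and the 12-month arm difference so adjusted is not in general the effect of assignment. This follows from the text and needs no numerical assumption.

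The size cannot be derived from the documents. It is zero if compliance is balanced or unrelated to outcome, about 0.05 to 0.10 AUC units under mild assumptions, and up to 0.67 under the strongest one tried. None of these is a bound, and the sign depends on both the arm gap and the compliance-outcome link. Even without bias, a 10-point gap would cost about 8 points of power (78% to 70%). Because this touches the primary result and is simple to remove, it must be fixed.

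**What to change.** - **SAP 5.1:** end the adjustment list at screening specific IgE, leaving age, gender, skin prick test and specific IgE.
- **SAP 7.2.1:** delete compliance from the predictors, so that the ITT models here and those inherited by 7.3, 7.3.1 and 7.3.2 use pre-randomisation covariates only. In the same edit, settle the baseline visual analogue scale, which 5.1 reserves for description and 7.2.1 treats as a predictor.
- **Compliance:** keep it for description by arm, the 75% per-protocol criterion, or a supportive analysis labelled as such.
- **Three-group comparisons:** add one sentence saying that analyses including the non-atopic controls do not adjust for compliance, skin prick test or specific IgE.

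The cost is SAP wording, with no change to data collection or sample size. It should be done before unblinding. The documents do not show whether that has taken place; if it has, the model without compliance should still be the ITT result, with the change documented.
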